2.2 Secondary Objectives

- 2.2.1 To determine whether 8 Gy x 2 fractions provides superior pain at 3 and 6 months post-treatment completion compared to 8 Gy x 1 fraction in solid tumor patients with bone metastases.
- 2.2.2 To determine whether 8 Gy x 2 fractions is associated with improved quality of life at 3 and 6 months post-treatment completion compared to 8 Gy x 1 fraction in solid tumor patients with bone metastases.
- 2.2.3 To determine if 8 Gy x 2 fractions is associated with increased toxicity.
- 2.2.4 To correlate patient satisfaction, perceived stress, and social support assessed via self-reported outcomes with treatment outcomes.

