4.3 Data Collection

At the time of enrollment, a detailed history and physical exam will be performed, including abstraction of patient vital signs and also documenting co-morbidities, patient demographics, age, gender, other medical conditions, and tumor characteristics. Other variables, such as education level, type of health insurance, and marital status (married/single/widowed/divorced/other) will also be obtained.

Blood Collection: Patients may consent to provide optional blood samples to be used for future genomic studies at baseline.

Prior Cancer Therapy: Information regarding the patient's history for anti-cancer therapy will be recorded.

Use of Bisphosphonates/Denosumab: Information regarding the patient's history for the use of bisphosphonates will be recorded. This will include the specific agent, dose, and date treatment started.

Changes in systemic chemotherapy, hormonal therapy, immunotherapy or the use of bisphosphonates for 4 weeks before and after the delivery of radiotherapy are allowed and will be recorded.

Pain level and Pain Medications: The patient's pain level will be assessed using the NRPS (detailed below). Information regarding the patient's history for the use of pain medications will be recorded. This will include the specific agent, dose, and date treatment started.

Nutrition Status, vitals, BMI: At each encounter, height (at baseline only), weight, Body Mass Index (BMI=kg/M²), and history of weight loss within three months prior to enrollment until patient's study completion will be recorded and/or extracted from patient records.

ECOG Performance Status

Patient Self-Reported Outcomes (SRO):

For evaluation of pain relief, the Numerical Rating Pain Scale (NRPS; Jensen 1999) will be used. The NRPS is a simple measure of pain on an 11-point scale (0-10). In the study comparing the reliability and validity of several measures of pain intensity, the composites of 0-10 ratings have been shown to be useful when maximal reliability was necessary in studies with relatively small sample sizes or in clinical settings in which monitoring of changes in pain intensity in individuals is needed. This will be performed prior to treatment and again at 1, 2, 3, and 6 months.

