For patients with a pain score >4 in the treated area at the 3 and 6 month follow-up, imaging (plain film, CT, bone scan, MRI) is recommended to assess for bone stability and pathologic fractures. Imaging should correlate with other imaging ordered by other treating physicians when possible. Coordination of all treatment and imaging should be collaborative to ease patient burden.

We will also include the following psychosocial measures at baseline and again at 3 and 6 months:

- European Organization for Research and Treatment of Cancer (EORTC) QLQ-C15-PAL
- Patient Satisfaction with Cancer Care (11)
- Perceived Stress Scale (12)
- Social Support (13)

Measurement of Treatment-Related Toxicities: Adverse events will be evaluated by the NCI Common Terminology Criteria for Adverse Event (CTCAE), v. 4.0. (14). Because of the patient population as well as the treatment, emphasis will be placed on gastrointestinal (GI disturbance, esophagitis, diarrhea, nausea, and vomiting), hematological (low blood counts or bleeding), spinal (bone fracture, compression fracture, insufficiency, or myelitis), and pulmonary toxicities (pneumonitis). However, all adverse events recorded by clinical research coordinators will be analyzed. Given the variety of non-protocol related treatment, toxicity will be assessed at 30 days after protocol treatment, as per DSMC requirements. These will be documented in Appendix I.

Focused Late AE Assessments: At 2, 3 and 6 months post-treatment, a focused AE assessment dependent upon the specific body area treated will be performed. These will be documented in Appendix I. Specific AEs to be collected will include the following:

- a) Fistula formation
 - a. Abnormal opening in the passageway from mouth to stomach (esophagus), bowels or bladder
- b) Scarring of the small or large bowel resulting in a blockage in the bowel that would require treatment
- c) Fracture of the bone within the radiotherapy treatment field (Fractures may require surgical treatment to prevent permanent disability).
- d) Temporary or permanent damage to the spinal cord, resulting in:
 - a. Skin sensations, such as burning, prickling, itching, or tingling
 - b. Muscle weakness causing inability to walk (paralysis)
 - c. Decreased ability or loss of ability to move a body part or to hold urine or control a bowel movement

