11.2 Analysis of Secondary Objective

There are several secondary outcomes of interest in this study. Most of these are measured on a continuous scale (i.e., quality of life by QLQ-C15-PAL, Patient satisfaction with cancer care, perceived stress scale) and thus will be compared between groups using 2-sample t-tests. In addition, the variable for pain response is categorical rather than continuous and will be compared at 3-months between groups using a Fisher's exact test. Patients categorized as Complete or Partial Responders will be compared with those categorized as stable or worsening pain responders.

Groups will also be compared to determine whether there are any differences in the number or severity of toxicities. When comparing severity of toxicities between groups, chi-square tests will be examined. The Cochran-Armitage trend test (in SAS Proc Freq) can be used to determine if there is evidence a trend in severity of toxicities when comparing groups.

In addition to the primary and secondary analyses described above, analyses will be performed that examine whether there are associations between quality of life, patient satisfaction and perceived stress measures and treatment outcome (re-treatment rates or amount of pain relief). In these

analyses, the outcome will be either re-treatment (yes/no) or amount of pain and predictors will include treatment arm, patient level measure and the treatment by patient level measure (i.e., QLQ-C15-PAL) interaction. For these analyses, either multiple logistic regression (for binary outcomes) models or analysis of covariance (ANCOVA) models for continuous outcomes will be used.

In these multiple logistic regression or ANCOVA models additional characteristics such as gender, whether the patient has weight-bearing (yes/no), ECOG performance status, number of lesions, or biophosphonates will also be considered as covariates in the models.

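### The association models in 11.2 aim at pain relief but take pain level as the outcome and do not name baseline pain, so a measure that only tracks pre-treatment pain can appear associated with treatment outcome

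*Combined protocol and SAP*

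**What the plan says.** Objective 2.2.4 is "To correlate patient satisfaction, perceived stress, and social support assessed via self-reported outcomes with treatment outcomes". Section 11.2 turns this into an examination of "associations between quality of life, patient satisfaction and perceived stress measures and treatment outcome (re-treatment rates or amount of pain relief"), so the continuous target is relief. The next sentence specifies the model: "the outcome will be either re-treatment (yes/no) or amount of pain and predictors will include treatment arm, patient level measure" and the interaction of the two. For the continuous case, "analysis of covariance (ANCOVA) models for continuous outcomes will be used".

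On further adjustment, 11.2 says that "additional characteristics such as gender, whether the patient has weight-bearing (yes/no), ECOG performance status, number of lesions, or biophosphonates will also be considered" as covariates. Baseline pain is not among the examples and is named nowhere else in section 11.

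The score is available. Section 4.3 says of the NRPS: "This will be performed prior to treatment and again at 1, 2, 3, and 6 months". Of the questionnaires it says: "We will also include the following psychosocial measures at baseline and again at 3 and 6 months". Section 11.2 does not say which visit supplies the pain outcome or which supplies the patient-level measure.

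**The concern.** Relief is a change from where the patient started; section 7.1 defines partial response partly as a fall of at least two points. Pain at follow-up is a level. If patients with high stress or poor quality of life enter with more pain, and some of that pain persists, the measure will correlate with follow-up pain even if it says nothing about how the patient fares from a given starting point. The model as listed cannot separate two statements: that stressed patients do worse after radiotherapy, and that stressed patients had more pain to begin with. Objective 2.2.4 asks about the first.

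For QLQ-C15-PAL some correlation with pain is built in, because items 5 and 12 in Appendix G ask about pain and its interference with daily life. Eligibility does not remove the variation in baseline pain: 3.1.5 admits scores from 5 to 10, and lower scores with sufficient opioid use.

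**Working it through.** **The plan's own figures.** The documents give no power or error rate for these models. The one design figure is the primary power, 0.80195. It reproduces: with 27.5 events and hazard ratio 0.5251, √27.5/2 × |ln 0.5251| − 0.8416 = 2.622 × 0.6442 − 0.8416 = 0.8475, and Φ(0.8475) = 0.802. It does not bear on this point.

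**Inputs.** From 11.3: 102 patients, 20% lost, 20% with a competing event. Evaluable number taken as 102 × 0.8 × 0.8 ≈ 65. Assumed, because the documents are silent: two-sided 0.05; the measure taken at baseline; correlation r1 between measure and baseline pain; correlation r2 between baseline and follow-up pain.

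**Null examined.** Follow-up pain is independent of the measure given baseline pain, and there is no arm effect.

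**Formula.** Under this null the measure still correlates r1 × r2 with follow-up pain. By the Fisher approximation, z = atanh(r1·r2) × √(65 − 3), and the rejection rate is P(Z > 1.96 − z) + P(Z < −1.96 − z). The simulated rates are from regressions of follow-up pain on arm (coded ±½), measure and interaction.

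| r1 | r2 | r1·r2 | z | Formula | Simulated, as written | Simulated, baseline pain added |
|---|---|---|---|---|---|---|
| 0.1 | 0.3 | 0.03 | 0.24 | 5.6% | 5.4% | about 5% |
| 0.1 | 0.5 | 0.05 | 0.39 | 6.8% | 6.9% | about 5% |
| 0.2 | 0.3 | 0.06 | 0.47 | 7.6% | 7.0% | 4.9% |
| 0.2 | 0.5 | 0.10 | 0.79 | 12.4% | 11.4% | 4.6% |
| 0.3 | 0.3 | 0.09 | 0.71 | 11.0% | 10.8% | 5.4% |
| 0.3 | 0.5 | 0.15 | 1.19 | 22.1% | 21.4% | 5.7% |
| 0.4 | 0.5 | 0.20 | 1.60 | 35.8% | 34.6% | 5.8% |

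**Arm coding.** With 0/1 coding the measure's coefficient is the slope in the reference arm alone, estimated from half the patients, so z is divided by √2. At 0.3/0.5: 1.190/1.414 = 0.842, giving 13% (simulated 14-15%). At 0.4/0.5: 1.596/1.414 = 1.129, giving 20% (simulated 20-21%). At 0.1/0.3 it is about 5%. The plan does not state the coding.

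**Other terms.** Arm is randomised, so tests of arm and of the interaction keep their level without baseline pain (simulated 4.4-5.9%).

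**Would change from baseline serve instead?** Not under this null. With raw change as outcome and no baseline covariate, the simulated rate is 23-99.6% over r1 of 0.3-0.7, r2 of 0.2-0.5 and 65-102 patients. Adding baseline pain to the follow-up model gives 4.0-6.4% over the same grid.

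**The case against.** **The text does not exclude baseline pain.** The covariates are examples, to be considered, and the pain-level wording may be shorthand for the relief just mentioned. A reader might infer that the plan forbids baseline adjustment; it does not. What stands is that the term that decides what the coefficient means is left optional while five others are named. The word ANCOVA does not supply it either: arm plus a continuous measure is already an ANCOVA.

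**The null is a choice.** Independence given baseline pain is not the same as no correlation with raw change. In the settings above the measure does correlate with raw change: r1(1 − r2)/√(2 − 2·r2) = 0.3 × 0.5/1 = 0.15 at 0.3/0.5, and 0.20 at 0.4/0.5. If the null is instead no correlation with raw change, the baseline-adjusted model rejects in 29% of trials at 0.3/0.5, 45% at 0.3/0.3 and 50% at 0.4/0.5. This objection stands. The 5% figure therefore shows that the adjusted model answers one well-defined question, not that it is valid for every meaning of relief. It does not rescue the listed model, which does worse under that null too.

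**The measure may be taken at follow-up.** If the 3- or 6-month questionnaire is the predictor, adjusting for baseline pain need not remove its link with pain at the same visit. This stands, so the visit has to be fixed as well.

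**These are association analyses.** Objective 2.2.4 asks to correlate, and 11.2 places these models in addition to its primary and secondary comparisons. An unadjusted association is a legitimate, less informative answer. That limits the importance of the point but does not remove the mismatch between aim and model.

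**Conclusion.** The point holds as a gap in the continuous pain model only. As listed, that model can attribute to treatment outcome what belongs to pre-treatment pain. Under the stated null, with 65 evaluable patients, a baseline measure and two-sided 0.05, the measure's main effect is rejected in about 5-35% of trials, or about 5-21% with 0/1 arm coding, against about 5% with baseline pain included. The correlations, evaluable number, significance level, coding and time point are all assumptions. At the lowest correlations there is practically no excess.

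A reader might infer that any measure tracking baseline pain will be declared associated, or that the arm comparisons are compromised. The documents support neither. The rate depends on correlations that they do not give, and the arm and interaction tests keep their level. The re-treatment model has no such switch of outcome, and the primary analysis and sample size are untouched. Nor does the argument carry over to the bone-agent model whose example outcome is relief yes/no, since response in 7.1 is already defined against a starting value.

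**What to change.** In 11.2, state the outcome as the follow-up NRPS score at a named visit and the patient-level measure as its baseline value. Make baseline NRPS a fixed covariate in every ANCOVA with continuous pain as outcome. Say that the measure's coefficient is read as association with follow-up pain given baseline pain. State the arm coding, so that it is clear whether the main effect is an average over arms or the slope in one arm. Replacing the outcome by raw change without the covariate would not be enough.

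In the exploratory bone-agent models, do the same only where pain is analysed on a continuous scale. Baseline daily morphine equivalents may likewise be added where continuous narcotic use is the outcome, as a gain in precision; no calculation here bears on that.

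The cost is a few sentences in 11.2 and one degree of freedom per model. Baseline NRPS and the baseline questionnaires are already collected.

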11.0 Statistical Considerations

11.1 Analysis of Primary Objective

This is a randomized Phase 2 study, with the primary objective to compare the 6-month cumulative incidence of re-treatment rates between groups. Based on previous research, the 8 Gy x 1 fraction [8/1] group (control group) had a retreatment rate of 18% (RTOG Study 97-14). The primary analysis will use a one-sided log-rank test statistic to test the null hypothesis that the re-treatment rates are equal in each group versus that alternative that the re-treatment rates are lower in the 8 Gy x 2 fractions [8/2] group. This analysis will account for competing risks such as death. Analyses will be performed on the patient level, thus if a patient has multiple metastases and any one of these requires retreatment then the patient will be considered retreated.

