For the exploratory outcome of examining the association between the use of a bone strengthening agent with pain relief, narcotic use and re-treatment rates either two-sample t-tests (if pain is measured on a continuous scale) or Fisher's exact tests (for categorical measures) will be used. In addition multiple logistic regression or ANCOVA models will be fit to look at the an outcome (i.e., pain relief yes/no) and the impact of bone strengthening agents (yes/no), number of metastases (one/more than one), treatment group (8/1 or 8/2) and the treatment by bone strengthening interaction.

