11.3 Power and Sample Size

Power calculations were performed using PASS 13. When accounting for competing risks, a one-sided logrank test with an overall sample size of 102 subjects (51 in the control group and 51 in the treatment group) achieves 80% power at a 0.2 significance level to detect a hazard ratio of 0.5251. The study is expected to last for 42 months with an accrual (entry) time of 36 months and a follow-up time of 6 months after the last patient is accrued. The cumulative incidence proportions at time 3 months for the event of interest are 0.18 in the control group (8/1) and 0.10 in the treatment group (8/2). The cumulative incidence proportions at time 6 months for the competing risk factors are 0.20 in the control group and 0.20 in the treatment group. The proportion of subjects lost to follow-up during the entire study is conservatively estimated at 0.2.

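### Re-treatment is modelled as yes/no by logistic regression with no rule for patients who die, enter hospice or are lost before 6 months, and with more candidate terms than the expected events support

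*Combined protocol and SAP*

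**What the plan says.** Section 11.1 makes the 6-month cumulative incidence of re-treatment the primary comparison, tested by a one-sided log-rank test, and adds: "This analysis will account for competing risks such as death".

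Section 11.2 then turns to associations between patient-reported measures and treatment outcome (objective 2.2.4): "analyses, the outcome will be either re-treatment (yes/no) or amount of pain and predictors will include treatment arm, patient level measure and the treatment by" measure interaction. The method is "either multiple logistic regression (for binary outcomes) models or analysis of covariance (ANCOVA) models" for continuous outcomes. On covariates, it says "additional characteristics such as gender, whether the patient has weight-bearing (yes/no), ECOG performance status, number of lesions, or biophosphonates will also be considered as covariates".

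For bone-strengthening agents (objective 2.3.1), the last paragraph of section 11.2 plans Fisher's exact tests for categorical measures. It also plans logistic or ANCOVA models with four named terms: agent, number of metastases, arm, and "the treatment by bone strengthening interaction". Its example outcome is pain relief, but re-treatment is among the outcomes it lists.

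Three other places bear on the data. Section 6.2.1 records cumulative re-treatment at the 6-month visit. Section 6.4 lets a patient leave the study on entering hospice. Appendix J asks only whether re-treatment occurred and the date of the first one.

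**The concern.** A yes/no outcome at 6 months is well defined only for a patient whose status at 6 months is known. Three groups lack an obvious value: those who die without re-treatment, those who leave for hospice, and those lost. The plan does not say whether they count as not re-treated, as missing, or as excluded. The predictors of interest (quality of life, ECOG status, bone-agent use) may plausibly be linked to survival. That link is a clinical assumption, not something the documents state. If it holds, the coding decides part of the answer.

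The second, separate problem is the number of terms. The covariate list is open, with no selection rule, no cap and no penalised estimation, and the expected number of re-treatments is small. This makes estimates imprecise and pushes them away from zero; it does not by itself push them in a protective direction.

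**Working it through.** **Inputs.** From section 11.3: 51 patients per arm, 20% loss, and "The cumulative incidence proportions at time 3 months for the event of interest are 0.18 in the control group (8/1) and 0.10 in the treatment" arm. The competing-risk incidence is 0.20 per arm, at 6 months in the text of section 11.3 but at time 3 in the software output after section 11.6. Both readings are carried through.

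**Reproducing the plan (software inputs).** With constant hazards, the total hazard is −ln(1 − F_event − F_competing)/3, split in proportion to the two incidences.
- 8/1 arm: −ln(0.62)/3 = 0.1593, giving 0.0755 (re-treatment) and 0.0839 (competing).
- 8/2 arm: −ln(0.70)/3 = 0.1189, giving 0.0396 and 0.0793.
- Hazard ratio: 0.0396/0.0755 = 0.525.

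These match the printed hazards and the 0.5251. The Schoenfeld formula at one-sided 0.2 and 80% power gives 27.3 events (printed 27.5), and 27.3/0.3399/0.8 = 100.4 patients (printed 102).

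**Incidence at 6 months, software inputs.**
- 8/1: 1 − 0.62² = 0.6156; re-treatment 0.6156 × 0.18/0.38 = 0.2916; competing 0.6156 × 0.20/0.38 = 0.324.
- 8/2: 1 − 0.70² = 0.51; re-treatment 0.51 × 0.10/0.30 = 0.170; competing 0.51 × 0.20/0.30 = 0.340.
- Re-treatments: 51 × (0.2916 + 0.170) = 23.5, or 18.8 after × 0.8 for loss.
- Competing events: 51 × (0.324 + 0.340) = 33.9, or 27.1 after loss.

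**Section 11.3 wording.** Solving for re-treatment 0.18/0.10 at 3 months and competing 0.20 at 6 months gives hazards 0.0712 and 0.0465 (8/1), and 0.0375 and 0.0419 (8/2). Re-treatment at 6 months is 0.306 and 0.179, so 24.7 events (19.8 after loss). Competing events are 102 × 0.20 = 20.4.

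**Effect of the coding.** Take a factor that doubles the competing hazard and leaves the re-treatment hazard alone. For the 8/1 arm on software inputs, the total hazard is 0.0755 + 0.1677 = 0.2432, the event-free proportion is exp(−6 × 0.2432) = 0.2324, and re-treatment is 0.0755/0.2432 × 0.7676 = 0.2382.
- Deaths counted as not re-treated: (0.2382/0.7618)/(0.2916/0.7084) = 0.76.
- Deaths before re-treatment excluded: (0.2382/0.2324)/(0.2916/0.3844) = 1.35.

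The same formulas elsewhere give:

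| Inputs, arm | Deaths as not re-treated | Deaths excluded |
|---|---|---|
| Software, 8/1 | 0.76 | 1.35 |
| Software, 8/2 | 0.79 | 1.32 |
| Section 11.3, 8/1 | 0.84 | 1.17 |
| Section 11.3, 8/2 | 0.87 | 1.15 |

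A factor that halves the competing hazard moves the other way (8/1, software). The event-free proportion is 0.4944 and re-treatment 0.3250, so the odds ratios are (0.3250/0.6750)/(0.2916/0.7084) = 1.17 and (0.3250/0.4944)/(0.2916/0.3844) = 0.87.

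**Events per term (software inputs).**
- Objective 2.2.4, three core terms: 18.8/3 = 6.3 to 23.5/3 = 7.8.
- Objective 2.2.4, all eight named terms (3 + 5): 18.8/8 = 2.4 to 23.5/8 = 2.9.
- Bone-agent model, four terms: 18.8/4 = 4.7 to 23.5/4 = 5.9.

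The section 11.3 wording gives 2.5-3.1 at eight terms.

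**Overfitting.** The eight-term model was simulated with n = 102 and 1,000 runs per scenario, with binary covariates split 50:50 (an assumption). The median arm log odds ratio was −0.75 to −0.79, against about −0.70 in large samples, so 7-13% too far from zero. Against the large-sample value with loss it is about 15% (0.78/0.68). The standard deviation was 0.60-0.67.

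**The case against.** The best defence is that a patient who dies without re-treatment has in fact not been re-treated by 6 months. Counting that patient as such matches the cumulative-incidence quantity in section 11.1, and an odds ratio of 0.76 misleads only if it is read as an effect on the need for re-treatment. That stands for deaths. It does not cover losses: a patient whose status is unknown is misclassified if counted as not re-treated, under any reading, and section 11.3 allows for 20% loss. Nor does the plan say that cumulative incidence is what these models estimate.

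The distortion is also modest beside the noise. For a 50:50 factor with 23.5 events in 102 patients, the standard error of a log odds ratio is about √(4/23.5 + 4/78.5) = 0.47, against ln 0.76 = −0.27. That is fair, but the gap between the two codings, ln(1.35/0.76) = 0.57, exceeds one standard error.

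It is right, too, that the five extra covariates are only to be considered, that these are secondary and exploratory analyses, and that the arm effect is judged by the primary test. These points limit the weight of the issue without removing it.

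**Conclusion.** The concern holds in a limited form. The stated binary model has no provision for death, hospice exit or loss. When a factor affects only mortality, neither way of handling deaths returns a null odds ratio, and the sign depends on which is used: 0.76-0.87 or 1.15-1.35 for a doubled death hazard. Separately, the largest named model for objective 2.2.4 would rest on 2.4-2.9 events per term.

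A reader might go further in four ways that the documents do not support:
- *That the plan codes the dead and the lost as not re-treated.* Appendix J makes this a likely default, but no rule is stated.
- *That prognostic factors in general will look falsely protective.* This applies to factors that raise mortality, under that one coding. Factors linked to longer survival move the other way, and factors unrelated to death stay near 1.
- *That every model has eight terms.* Eight is the most that section 11.2 names for objective 2.2.4; three are fixed, and the bone-agent model names four.
- *That objectives 2.2.4 and 2.3.1 cannot be answered.* Both also cover pain, which this argument does not touch.

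The figures assume constant hazards and the plan's own inputs; the twofold effect on death is illustrative. The low event count multiplies by 0.8 for loss, although some lost patients would have been re-treated first. The primary test is unaffected.

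**What to change.** For re-treatment, replace the logistic model, and Fisher's exact test for bone agents, with a cause-specific Cox model. Use the Appendix J date of first re-treatment and censor at death or last contact. Show cumulative incidence by level of the factor, or a Fine-Gray model, alongside, so that the hazard and the 6-month risk are both visible. State how hospice exit is treated; censoring there assumes that leaving is unrelated to later re-treatment, and the report should say so.

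Pre-specify arm, the measure, their interaction and at most one or two further covariates. Use baseline values of the measure and of bone-agent use: section 4.3 also collects the questionnaires at 3 and 6 months, and a later value would need a landmark or time-dependent analysis.

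The cost is a change of wording in section 11.2 and fewer covariates adjusted for at once. Death and last-contact dates must be available, but the competing-risk primary analysis already needs them.
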